8.3.8 Second primary malignancies

AEs for malignant tumors reported during a study should generally be assessed as SAEs. If no other seriousness criteria apply, the "Important Medical Event" criterion should be used. In certain situations, however, medical judgment on an individual event basis should be applied to clarify that the malignant tumor event should be assessed and reported as a nonserious AE. For example, if the tumor is included as medical history and progression occurs during the study but the progression does not change treatment and/or prognosis of the malignant tumor, the AE may not fulfil the attributes for being assessed as serious, although reporting of the progression of the malignant tumor as an AE is valid and should occur. Also, some types of malignant tumors, which do not spread remotely after a routine treatment that does not require hospitalization, may be assessed as nonserious; examples in adults include Stage 1 basal cell carcinoma and Stage 1A1 cervical cancer removed via cone biopsy.

The above instruction applies only when the malignant tumor event in question is a new malignant tumor (i.e., it is not the tumor for which entry into the study is a criterion and that is being treated by the investigational product under study and is not the development of new or progression of existing metastasis to the tumor under study). Malignant tumors that—as part of normal, if rare, progression—undergo transformation (e.g., Richter's transformation of B-

cell chronic lymphocytic leukemia into diffuse large B-cell lymphoma) should not be considered a new malignant tumor.

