## 1.2 Study Design

This randomized, regional, multicenter, open-label, Phase 3 study will evaluate the efficacy and safety of acalabrutinib monotherapy (Arm A) versus chlorambucil plus rituximab (Arm B) in patients with previously untreated Chronic Lymphocytic Leukemia (CLL) without del(17p) or TP53 mutation.

[figure not shown]
Study assessments will be conducted in accordance with the schedule of assessments, which can be found in the CSP, section 1.1. See Figure 1 below for a graphical representation of the study design.

Patient participation will include a screening phase, treatment phase, post-treatment disease follow-up phase, and survival follow-up phase. The screening phase will last up to 28 days before the first dose of study drug, during which the patient's eligibility and baseline characteristics will be determined. The treatment phase will last from randomization until study drug(s) discontinuation for the purpose of efficacy analyses, and from first dose to study drug(s) discontinuation for safety analyses. Treatment with acalabrutinib may be continued until disease progression or any other treatment discontinuation criterion is met. Treatment with chlorambucil/rituximab includes maximum 6 cycles, or until there is disease progression or any other treatment discontinuation criterion is met. In both treatment arms a cycle is defined as 28 days ( $\pm 3$  days for Arm B).

Patients randomized to Arm B who have blinded independent central review (BICR) confirmed disease progression may be eligible to crossover and receive single agent acalabrutinib 100 mg BID at investigator discretion provided they meet the crossover eligibility criteria, as defined in the CSP. An end of treatment (EoT) visit is required for safety assessments for any patients who permanently discontinue study drug for any reason (except for death, lost to follow-up, or withdrawal of consent), including disease progression. The EoT visit should be performed within 7 days of the last dose of all study drugs, if possible, and is not required for patients who discontinue from study drug within 10 days of a scheduled study visit, or if the EoT visit would be performed within 14 days of the safety follow-up (SFU) visit.

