### 3.5.2 Adverse events

AEs will be collected throughout the study, from date of informed consent until 30 days after the last dose of study drug. SAEs will be collected from the date of informed consent. The following events will be considered treatment emergent:

- Adverse events with an onset date on or after first dose of study drug, and within 30 days after last dose of study drug or the initiation of a subsequent therapy (including crossover treatment), whichever occurs first.
- Worsening of pre-existing events on or after first dose of study drug, and within 30 days after last dose of study drug or the initiation of a subsequent therapy (including crossover treatment), whichever occurs first.

The Medical Dictionary for Regulatory Activities (MedDRA) (using the latest or current MedDRA version) will be used to code the AEs. AEs will be graded according to the

National Cancer Institute Common Terminology Criteria for AEs (using the NCI CTCAE version 5.0).

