#### 4.2.6 Safety

All safety summaries will use the safety analysis set. Safety analyses, except for death, will include data only prior to crossover for patients from Arm B. Selected outputs will be repeated for the crossover period.

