#### 4.2.6.1 Exposure

Summary statistics will be calculated for total exposure, actual exposure and RDI for each study drug. Additionally, a categorical summary of RDI will be produced, with categories < 80%, 80 – 120% and > 120%.

For patients who received acalabrutinib monotherapy, dose withholding and dose reduction will be summarized along with the reasons. For patients who received rituximab, dose delay and infusion interruption will be summarized along with the reasons. For patients who received Chlorambucil, dose interruption (defined as skip one or more dose in one cycle), dose delay and dose reduction will be summarized along with the reasons. Acalabrutinib dose reduction is defined as taking lower dose level (100 mg QD) for  $\geq 3$  consecutive days, dose withholding is defined as missing dose for  $\geq 7$  consecutive days.

Total exposure, actual exposure, RDI and dose modifications will also be analyzed for the crossover period.

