#### 4.2.6.2 Adverse events (AEs)

All TEAEs, both in terms of current MedDRA preferred term and NCI CTCAE grade, will be summarized descriptively by count (n) and percentage (%) for each treatment group. The current MedDRA dictionary will be used for coding.

An overall summary of the number and percentage of patients in each of the following categories will be presented:

- All treatment emergent adverse events (AEs)
- All related AEs
- AEs with outcome of death
- Related AEs with outcome of death
- Serious AEs (SAEs)
- Related SAEs
- AEs leading to discontinuation of IP
- Related AEs leading to discontinuation of IP
- AEs leading to IP dose interruptions/delays\*
- Related AEs leading to IP dose interruptions/delays\*
- AEs leading to IP dose reduction

- Related AEs leading to IP dose reduction

\*AE leading to dose delay only applies to Arm B.

The overall summary will be repeated for the crossover period.

All AEs will be listed, including AEs which are reported more than 30 days after last dose. AEs which occur after the first dose of crossover therapy will be flagged in the listings as well as AEs which occur after the initiation of any other subsequent therapies.

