### **Serious adverse events (SAEs) and drug-related SAEs**

SAEs and drug-related SAEs will be summarized by SOC and PT in descending order of frequency. SAEs will also be listed separately.

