### **Events of clinical interest (ECI)**

ECIs are defined in section 3.5.2. A summary of the number and percentage of patients with ECIs will be provided by ECI category and ECI subcategory. In addition, for each ECI category, a separate summary table will be displayed with number and percentage of ECIs by ECI subcategory and Preferred Term. Refer to [Appendix A](#) for ECI.

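### Second primary malignancies are tabulated only as crude percentages, apparently over treatment-emergent windows about four times longer in Arm A than in Arm B, with no patient-year rate

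*SAP*

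**What the plan says.** Protocol 2.3.1.1 lists SPM among the important identified risks of acalabrutinib, and SAP 3.5.2 names it as an ECI category. On reporting, the ECI paragraph of SAP 4.2.6.2 says: "A summary of the number and percentage of patients with ECIs will be provided by ECI category and ECI subcategory". The general rule in the same section is that treatment-emergent events "will be summarized descriptively by count (n) and percentage (%) for each treatment group". I found no patient-years, incidence rate or time-to-event analysis for any adverse event in the visible SAP.

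SAP 3.5.2 defines an event as treatment-emergent if it starts on or after first dose and "within 30 days after last dose of study drug or the initiation of a subsequent therapy (including crossover treatment), whichever occurs first". SAP 4.2.6 adds: "Safety analyses, except for death, will include data only prior to crossover for patients from Arm B".

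Treatment length differs by design. SAP 1.2 says "Treatment with chlorambucil/rituximab includes maximum 6 cycles, or until there is disease progression", whereas acalabrutinib continues until progression or another stopping criterion.

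Four other planned outputs bear on the point:
- **Exposure** (SAP 4.2.6.1): "Summary statistics will be calculated for total exposure, actual exposure and RDI for each study drug".
- **Serious events.** Protocol 8.3.8 says "AEs for malignant tumors reported during a study should generally be assessed as SAEs", and in the SAP "SAEs and drug-related SAEs will be summarized by SOC and PT in descending order of frequency". No window is given for that table.
- **Post-treatment events.** Protocol 9.5.2 plans to present pre-treatment, treatment-emergent and post-treatment events separately. SAP 4.2.6.2 says that events reported more than 30 days after last dose will be listed.
- **Malignancies after progression.** Protocol 7.1.2 and SAP 1.2 record them in survival follow-up, at contacts about 24 weeks apart. The visible SAP names no summary of that item by arm.

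**The concern.** A percentage of patients with an event is comparable between arms only if the arms are observed for similar lengths of time. Here one arm stops treatment after six cycles and the other is treated to progression, and the treatment-emergent window follows treatment. Malignancies accrue with time at risk, so the arm observed longer will show more of them even if the drug has no effect.

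At stake is how an identified risk is read. Someone looking at the ECI table could take unequal observation time for an effect of acalabrutinib. The distortion runs against the investigational drug, but it would be just as unwelcome in the other direction: with crude percentages, a true excess cannot be separated from the excess that the design produces.

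**Working it through.** **Inputs from the documents.** 75 patients per arm, exponential PFS with medians of 30 and 90 months, accrual over about 30 months, planned analyses at months 40 and 53 (Protocol 9.2, SAP 1.3). The final analysis took place at about month 45 (Protocol 4.4). Cycles last 28 days (SAP 1.2), and the last Arm B dose is chlorambucil on Cycle 6 Day 15 (Protocol 6.1.2).

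**Assumptions of this check.** Uniform accrual; Arm A treated to progression; an alternative Arm A median of 60 months; an alternative in which 10% per year also stop for other reasons; no separate term for dropout.

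**The plan's own figures.** The documents state no safety-window length. Their power claim reproduces: Φ(1.0986 × √50 / 2 − 1.960) = Φ(1.924) = 97.3%, against a stated value above 95%. At month 45 the model expects 52.1 PFS events without dropout, or 49.5 with the SAP's 5% dropout by 14 months. The protocol reports 48 observed, so the model is close at the date that matters. It is faster than the plan at months 40 (43–45 events against 38) and 53 (58–62 against 50).

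**Arm B window.** Cycle 6 Day 15 is day 5 × 28 + 15 = 155. Adding 30 gives day 185, or 6.1 months. Person-time: 75 × 185 / 365.25 = 38.0 patient-years (PY). Early stopping shortens this and dose delays lengthen it.

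**Arm A window.** For follow-up of t months and stopping hazard L per month, the expected window including a one-month tail is 1 + (1 − exp(−L(t − 1)))/L, averaged over t uniform on (T − 30, T). For T = 45 and median 90:
- L = ln 2 / 90 = 0.007702
- mean of exp(−L(t − 1)) = (0.8978 − 0.7126)/(30 × 0.007702) = 0.8016
- window = 1 + (1 − 0.8016)/0.007702 = 26.8 months
- person-time = 75 × 26.76 / 12 = 167.2 PY
- ratio = 167.2 / 38.0 = 4.4

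For 10% per year other stops, add −ln(0.9)/12 = 0.00878 to L. Values for median 90, with median 60 in brackets:

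| Analysis | Other stops | Window, months | Ratio A:B |
|---|---|---|---|
| Month 40 | none | 22.7 (21.6) | 3.7 (3.6) |
| Month 40 | 10%/year | 20.4 (19.5) | 3.4 (3.2) |
| **Month 45** | none | 26.8 (25.3) | 4.4 (4.2) |
| **Month 45** | 10%/year | 23.7 (22.5) | 3.9 (3.7) |
| Month 53 | none | 33.0 (30.8) | 5.4 (5.1) |
| Month 53 | 10%/year | 28.4 (26.6) | 4.7 (4.4) |

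The four month-45 rows correspond to 167.2, 158.3, 147.9 and 140.5 PY.

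**What equal hazards would look like.** The documents give no SPM rate, so assume 2 per 100 PY in both arms (range 1–4), at month 45 with median 90 and no other stops. Expected patients with at least one SPM are 3.3 in Arm A (1.7–6.4) and 0.8 in Arm B (0.4–1.5). At 2 per 100 PY the ratio of patients is about 4.3, slightly below the person-time ratio. With Poisson counts of mean 167.2r and 38.0r, Arm A shows more cases with probability 86% (70–96%) and Arm B with probability 5% (8–2%).

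**Percentage against rate.** Suppose 1 patient in Arm B and 3 in Arm A. Crude: 1.3% against 4.0%. As rates: 1/38.0 = 2.6 per 100 PY (exact 95% CI 0.07–14.7) against 3/167.2 = 1.8 (0.4–5.2). The direction reverses, and both intervals are very wide.

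**The case against.** Five things can be said for the plan.

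1. **Safety is descriptive.** The protocol synopsis says safety data will not be formally analysed, and no decision rule uses the SPM percentage. This stands, and it limits the severity.
2. **Person-time can nearly be recovered.** Mean exposure times N, plus a 30-day tail, approximates it. True, but the exposure tables are by drug, and no planned output divides cases by time at risk, so the reader of the ECI table is left to do it.
3. **Late events are not ignored.** A reader might infer that malignancies after the treatment window have no planned presentation. The documents do not support that: Protocol 9.5.2 presents post-treatment events separately, the SAP lists late events, and the serious-event tables state no window. What remains is that none of these gives a rate. In addition, Protocol 8.3.1 narrows collection after 30 days to related serious events and events of concern.
4. **The window is inferred.** The ECI paragraph names none, and Appendix A is not in the text reviewed. This stands, and the point is worded accordingly.
5. **A rate has its own weakness.** It compares roughly the first 6 months in Arm B with two years or more in Arm A, so it needs a roughly constant hazard, which is a strong assumption for malignancy. With so few cases, one or two can reverse the direction. This stands and belongs in a footnote; it does not make the crude percentage the better summary.

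**Conclusion.** The point holds as a cheap improvement to reporting. As written, SPM is summarised by n (%) only, apparently over windows of at most about 6 months in Arm B and about 22 to 27 months in Arm A at the actual final analysis. That is a person-time ratio of about 3.7 to 4.4, or about 3.2 to 5.4 across all dates and stopping assumptions in the table. At equal hazards the percentages would show several times more SPM patients in Arm A.

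The size rests on uniform accrual, exponential PFS at the design medians, and an assumed rate of stopping for other reasons. Back-loaded accrual would shorten the Arm A window. The 5.4 end belongs to a month-53 analysis that did not take place and should not be used as the headline.

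Three stronger readings are not supported. The documents do not show that any SPM excess in Arm A would be spurious; they show only that the planned table could not tell. They do not support a rate for time after progression, because no visible text says that an onset date is collected for that item. And nothing here touches the primary PFS analysis.

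**What to change.** In SAP 4.2.6.2 add one descriptive SPM table by arm, labelled supplementary and post hoc because the final analysis has been done and the study unblinded. For the treatment-emergent period, and separately for the crossover period, give:
- n (%) of patients with an SPM;
- patient-years from first dose to first SPM or end of window;
- rate per 100 patient-years with exact 95% CI.

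State the window used for the ECI table. Footnote that few cases are expected and intervals are wide, that comparing rates over unequal windows assumes a roughly constant hazard, and that collection after treatment is limited.

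Report malignancies recorded in survival follow-up after progression as counts by arm, with crossover patients shown separately. Compute a rate for them only if onset dates were collected. Even then it could not be attributed to the randomised drug, because that time mixes untreated time with other anti-CLL therapy.

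The cost is one table from dosing and event dates already held, with no change to endpoints, alpha or data collection. The drawbacks are that it is post hoc and imprecise.

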### **AEs and drug-related AEs**

AEs and drug-related AEs will be summarized by system organ class (SOC) and preferred term (PT) in descending order of frequency and separately by maximum NCI CTCAE toxicity grade. In addition, AEs with NCI CTCAE grade  $\geq 3$  and drug-related AEs with NCI CTCAE grade  $\geq 3$  will be summarized by SOC and PT. An additional table will present the number and percentage of patients with AEs by PT.

AEs will also be summarized separately for the crossover period by SOC and PT. Further AE summaries may be produced for the crossover period in an exploratory fashion if sufficient AEs occur to make these summaries worthwhile.

### **Serious adverse events (SAEs) and drug-related SAEs**

SAEs and drug-related SAEs will be summarized by SOC and PT in descending order of frequency. SAEs will also be listed separately.

### **AEs and drug-related AEs leading to treatment discontinuation**

AEs and drug-related AEs leading to treatment discontinuation will be summarized by SOC and PT in descending order of frequency. AEs leading to treatment discontinuation will also be listed separately.

### **AEs leading to dose interruptions/delays and reduction**

AEs leading to dose interruptions/delays and dose reduction, as indicated in the eCRF will be summarized by SOC and PT in descending order of frequency.

### **AEs leading to death and drug-related AEs leading to death**

AEs leading to death and drug-related AEs leading to death will be summarized by SOC and PT in descending order of frequency. AEs leading to death will also be listed separately.

### **Adverse events of special interest (AESI)**

A summary table of certain MedDRA preferred terms will be produced and will also show the individual preferred terms which constitute each AESI grouping. AESIs will also be summarized by PT.

### **Events of clinical interest (ECI)**

ECIs are defined in section 3.5.2. A summary of the number and percentage of patients with ECIs will be provided by ECI category and ECI subcategory. In addition, for each ECI category, a separate summary table will be displayed with number and percentage of ECIs by ECI subcategory and Preferred Term. Refer to [Appendix A](#) for ECI.

### **Analyses for crossover period**

Summary tables from the above AE section, including AEs, AEs leading to death, AEs leading to dose discontinuation, serious AEs, and overall summary of ECIs, will be repeated for patients in the crossover period, provided the crossover period includes at least 10 patients. Otherwise, crossover related safety data will be listed only.

The AE summary tables for crossover patients will include all AEs that occurred after the start of crossover treatment up until the end of the 30 day follow-up period. The 30 day follow-up period will be defined as 30 days following discontinuation of treatment.

In addition to AE summaries, selected summaries of clinical laboratory parameters, vital signs and ECG data might be repeated for crossover patients only provided at least 10 patients receive crossover therapy.

#### **4.2.6.3 Clinical laboratory data**

Laboratory data obtained until 30 days after the last dose of study treatment or the start of a subsequent therapy (including crossover treatment), whichever occurs first, will be used for reporting. Project-specific reference ranges will be applied for relevant laboratory variables (hematology, clinical chemistry).

Hematology, clinical chemistry, T/B/NK Cell Count and Serum Immunoglobulin will be listed individually by patient and suitably summarized and may be plotted as needed. Patients who received IVIG on the study will be excluded from the summary for IgG. For all laboratory variables, which are included in the version 5.0 of NCI CTCAE, the NCI CTCAE grade will be calculated.

Numerical laboratory data (absolute and change from baseline) will be summarized by scheduled visit using standard summary statistics (mean, standard deviation, minimum, median, maximum, and number of observations).

For hematology and clinical chemistry, where applicable, data shift tables will summarize the change from baseline to maximum on-treatment NCI CTCAE grade, the change from baseline to maximum value, and the change from baseline to minimum value.

Central laboratory data will be used for summaries of hematology, however local laboratory data will be used when central data is not available. All laboratory hematology data will be summarized together, regardless of whether the tests were performed for safety purposes or for evaluation of disease response. Summary of T/B/NK cell count will be based on central laboratory data. Summaries of clinical chemistry and serum immunoglobulin levels will use local laboratory data.

To identify potential Hy's Law (see CSP Appendix D for further details) cases, patients who meet any of the following criteria at any point during the study will be highlighted:

- $AST \geq 3 \times ULN$
- $ALT \geq 3 \times ULN$
- $TBL \geq 2 \times ULN$

For all patients who meet the biochemical criteria for Hy's Law (potential Hy's Law), the relevant laboratory parameters will be tabulated showing all visits for these patients.

Any data outside the laboratory reference ranges will be flagged and explicitly noted on the listings that are produced. To help identify potential Hy's Law cases, patients who have  $ALT$  or  $AST \geq 3 \times ULN$  or total bilirubin  $\geq 2 \times ULN$  at any time during the study (i.e. not necessarily at the same time) will be flagged in the listings.

All laboratory results will be listed.

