- a. Subjects who stop both drugs early because of an adverse event and disease progression has not occurred at that time, will then enter an Post-treatment disease follow up phase. Post-treatment disease follow-up visits should occur approximately every 12 weeks or 24 weeks from the date of last disease evaluation until disease progression, regardless of whether the subject receives a new anticancer therapy.
- b. An end of treatment visit will be done within 7 days for subjects who permanently discontinue study drugs early for any reason (except for death, lost to follow-up, or withdrawal of consent), including disease progression. See detail in Section 7.1.1. A safety follow-up visit is conducted 30 days (+7 days) after the last dose of study drug, regardless of whether the subject receives a new anticancer therapy or demonstrates disease progression within this timeframe. If the safety follow-up visit is within ± 7 days of a regularly scheduled visit during the Post-treatment Phase, the visits may be combined into a single visit.
- c. Response evaluations will be done every 12 weeks (± 14 days) with the first on-treatment assessment occurring on Cycle 4 Day 1, the second on Cycle 7 Day 1, and so on through Cycle 25. After Cycle 25 response evaluations will be done every 24 weeks (± 14 days) thereafter, until disease progression. For additional details on the confirmatory bone marrow biopsy for subjects in Arm B, see Minimal Residual Disease/Response Evaluation in Section 8.1.2.
- d. Hepatitis serology must include hepatitis B surface antigen (HBsAg/HbsAg), hepatitis B surface antibody (anti-HBs), hepatitis B core antibody (anti-HBc), and hepatitis C (HCV) antibody.
- e. After the end of the protocol-defined adverse event reporting period (Section 8.3.1), only serious adverse events considered related to study drug(s) or study procedures are required to be collected.
- f. Women of childbearing potential only. A urine or serum pregnancy test is acceptable. Pregnancy testing can be done more frequently than the protocol-defined schedule.

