6.7 Treatment after the end of the study

No intervention for patients is planned after the end of the study. However, provisions will be in place for patients still enrolled at the end of the trial to continue to receive study intervention if, in the opinion of the investigator, they are continuing to receive benefit from treatment.

In the event that a roll-over or safety extension study is available at the time of the database closure, patients currently receiving treatment with study intervention may be transitioned to such a study, and the current study would reach its end. Patients in Arm B will still be allowed to cross over to receive acalabrutinib as specified in section 6.7. The roll-over or safety extension study would ensure treatment continuation with visits and assessments per its protocol. Any patient who would be proposed to move to such a study would be asked to sign a new ICF.

Such subjects who are still receiving or will cross over to receive acalabrutinib will continue to be monitored for all AEs up to 30 (+7) days after the last dose of investigational product. For subjects who do continue to receive treatment beyond the closure of the database, investigators will continue to report all SAEs to the sponsor Patient Safety until 30 days after IP is discontinued, in accordance with Section 8.4.1(Reporting of SAEs).

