7.1.1 Procedures for discontinuation of study treatment

The investigator should instruct the subject to contact the site before or at the time if study treatment is stopped. A subject that decides to discontinue study treatment will always be asked about the reason(s) and the presence of any AEs. The date of last intake of study treatment should be documented in the eCRF. All study treatment should be returned by the subject at their next on-site study visit or unscheduled visit. Subjects permanently discontinuing study treatment should be given locally available standard of care therapy, at the discretion of the investigator.

Discontinuation of study treatment, for any reason, does not impact on the subject's participation in the study. The subject should continue attending subsequent study visits and data collection should continue according to the study protocol. Patients who have

permanently discontinued from further receipt of IP will need to be discontinued from the IRT/RTSM.

An EoT visit is required for safety assessments for any subjects who permanently discontinue study treatment for any reason (except for death, lost to follow-up, or withdrawal of consent), including disease progression. The end of treatment visit is not required for subjects who discontinue from study treatment within 10 days of a scheduled study visit or if the EoT visit would be performed within 14 days of the safety follow-up visit. If the SFU visit is within ± 7 days of a regularly scheduled visit during the post-treatment phase, the visits may be combined into a single visit.

In addition to the EoT visit, an SFU visit should be conducted at 30 (+7) days after his or her last dose of all study drugs to monitor for resolution or progression of AEs and to document the occurrence of any new events, regardless of whether the subject receives a new anticancer therapy or demonstrates disease progression within this time frame. Refer to Tables 1-3, for the assessments required for the EoT and SFU visits.

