#### **4.2.6.4 Vital signs**

Summaries of vital signs data will include all data obtained until 30 days after the last dose of study treatment or the start of a subsequent therapy (including crossover treatment), whichever occurs first. Pulse rate, systolic and diastolic blood pressure, body temperature, respiratory rate and weight will be listed by patient and summarized using standard summary statistics for the absolute value and change from baseline at each visit.

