#### **4.2.6.5 ECOG performance status**

Summaries of ECOG data will include all data obtained until 30 days after the last dose of study treatment or the start of a subsequent therapy (including crossover treatment), whichever

occurs first. The number (%) of patients fulfilling each ECOG performance status category will be presented for each visit.

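### The safety follow-up visit is due 30 to 37 days after the last dose, but the laboratory, vital-sign and ECOG summaries stop at day 30, which exposes Arm B more than Arm A

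*SAP*

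**What the plan says.** **Visit timing.** Protocol 7.1.1 states that "an SFU visit should be conducted at 30 (+7) days after his or her last dose of all study drugs". The Arm B schedule footnote in protocol 1.1 agrees: "A safety follow-up visit is conducted 30 days (+7 days) after the last dose of study drug". The Arm A and crossover footnotes use the same one-sided window. The EoT/SFU column of the schedules includes safety measurements such as hematology and chemistry. Protocol 7.1.1 gives the purpose of the visit as following known AEs and picking up new ones.

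**Analysis window.** Three SAP sections stop at day 30, or earlier if subsequent or crossover therapy starts:
- 4.2.6.3: "Laboratory data obtained until 30 days after the last dose of study treatment or the start of a subsequent therapy".
- 4.2.6.4: "Summaries of vital signs data will include all data obtained until 30 days after the last dose of study treatment".
- 4.2.6.5: "Summaries of ECOG data will include all data obtained until 30 days after the last dose of study treatment".

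Protocol 9.4.2 sets the same 30-day limit for its on-treatment period. The SAP therefore follows the protocol's analysis text, and the mismatch is with the visit window.

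**Adverse events.** Treatment emergence in SAP 3.5.2 depends on onset: "Adverse events with an onset date on or after first dose of study drug, and within 30 days after last dose of study drug". SAP 4.2.6.2 adds: "All AEs will be listed, including AEs which are reported more than 30 days after last dose".

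**The concern.** The visit cannot take place before day 30, yet the summaries accept nothing after day 30. A site that holds the visit on any of the following seven permitted days complies fully with the protocol, but its values are left out of the by-arm tables. SAP 4.2.4 also says that visit windows are exhaustive, so that data from any time can be summarized. A hard day-30 cut fits poorly with that.

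The tables at stake include the shifts to maximum on-treatment CTCAE grade and to maximum and minimum values. Adding a visit can only leave a patient's worst grade unchanged or make it worse, so leaving the visit out can only lower the worst-grade counts. Hematologic toxicity is where this would matter most: protocol 4.2 reports that it accounted for most Grade 3-4 events with this comparator in an earlier phase 2 study. Under protocol Table 13, a non-serious AE after day 30 is not reported unless it is of concern. For an abnormality first seen on days 31 to 37, the laboratory summary is therefore the main by-arm table in which it could appear.

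**Working it through.** The documents state no figure on this point, so there is none to reproduce.

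**1. Window against cut (both arms).** Permitted SFU days are 30, 31, ..., 37, which is 8 days. Days after the cut are 31 to 37, which is 7 days, and 7/8 = 87.5%. If "Laboratory data obtained until 30 days after the last dose of study treatment or the start of a subsequent therapy" is read as excluding day 30 itself, the count is 8 of 8.

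**2. Share of visits lost.** This equals 1 minus the share held on day 30. The distribution of visit dates is not given, so the following are assumptions:

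| Share of SFU visits held on day 30 | Share lost from the summaries |
|---|---|
| 12.5% (even spread) | 87.5% |
| 25% | 75% |
| 50% | 50% |
| 75% | 25% |

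**3. Arm B calendar.** Inputs: 28-day cycles and chlorambucil on Days 1 and 15 of Cycles 1 to 6 (protocol Table 6).
- Last planned dose, Cycle 6 Day 15: 5×28 + 15 = study day 155.
- SFU window: 155 + 30 = 185 to 155 + 37 = 192. The cut is at 185.
- Cycle 7 Day 1: 6×28 + 1 = 169, which is 14 days after the last dose and so inside the cut.
- Cycle 10 Day 1: 9×28 + 1 = 253.

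Protocol 7.1.1 allows the SFU to be merged with a scheduled visit within ±7 days. For a patient on schedule, the nearest visits are 185 − 169 = 16 days before the window opens and 253 − 192 = 61 days after it closes, so merging does not apply. The window closes at about 192/30.4 = 6.3 months, and essentially every followed Arm B patient reaches it before the analysis.

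There is an exception. If the Cycle 6 Day 15 dose is skipped for cytopenia (protocol 6.6.2), the last dose is on day 5×28 + 1 = 141. Cycle 7 Day 1 (±3) then falls 169 − 141 = 28, that is 25 to 31, days after it. It can be merged with the SFU and is inside the cut on 6 of those 7 days.

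**4. Arm A exposure.** An SFU visit arises only when acalabrutinib stops, and the documents give no discontinuation rate. To see what the design implies, take exponential PFS with a median of 90 months (λ = ln 2/90 = 0.00770 per month), uniform accrual over 30 months, and analysis at T months. The share with a PFS event is 1 − [exp(−λ(T−30)) − exp(−λT)]/(30λ).
- T = 45: 1 − (0.891 − 0.707)/0.231 = 20%.
- The same formula gives 17% at T = 40 and 25% at T = 53.

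As a check on these inputs, the same model with Arm B at a median of 30 months gives 52.1 events at 45 months without dropout, and 49.5 with the SAP's 5% dropout by 14 months. Protocol 1.2 reports 48 events at the final analysis, which protocol 4.4 places at about 45 months.

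Now assume that 0% to 30% stop for other reasons by 24 months and add that hazard to λ. The share off treatment becomes 20% to 48% at 45 months and 25% to 57% at 53 months. PFS events include deaths, and patients who die have no SFU visit, so these figures indicate exposure and are not visit counts.

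**5. After the change.** With the cut at day 37, all 8 permitted days are inside.

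**The case against.** A reader might infer that the plan discards safety data from this visit. It does not:
- AEs are classified by onset date, so an event that began by day 30 and is first recorded on day 37 still counts as treatment-emergent.
- Late AEs and all laboratory results are listed.
- The Hy's Law screen is worded to cover any point in the study.
- No day-30 cut is stated for the ECG listings or the physical-examination shift table.
- Related SAEs and AEs of concern remain reportable after day 30.

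A reader might also infer that nearly every Arm B patient loses the visit. What the schedule shows is that nearly every followed Arm B patient has a visit exposed to the cut. Day 30 is the nominal date, and a merged visit after a skipped dose is mostly kept.

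Finally, the analysis of safety is descriptive, Cycle 7 Day 1 data are retained, and up to seven extra days is small beside the difference between six cycles and open-ended treatment. These points limit the importance of the mismatch but do not remove it. Listings are not a by-arm comparison, and for Arm B patients on schedule no other visit replaces the excluded one.

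Protocol 6.7 might be cited as a precedent for a longer AE window, since such patients "will continue to be monitored for all AEs up to 30 (+7) days after the last dose of investigational product". That section covers patients treated beyond the end of the study, and the same paragraph uses a plain 30 days for SAEs. It does not justify redefining treatment emergence here.

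**Conclusion.** The mismatch stands for the laboratory, vital-sign and ECOG summaries and the worst-grade shift tables. Seven of the eight permitted SFU days lie outside the cut. The loss is 87.5% of visits under an even spread, 50% if half are held on day 30 and 25% if three quarters are.

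Arm B is the more exposed arm because its treatment is fixed at six cycles. Any effect on worst-grade counts is therefore more likely to understate late Arm B abnormalities. The documents do not allow that effect to be sized for any table. It might also be inferred that only a minority of Arm A patients are affected, but the documents do not show this. It holds at 45 months over the discontinuation range assumed above, and fails at 53 months once other discontinuation reaches about 25% by 24 months.

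This is a cheap improvement to the reporting and does not threaten the trial's conclusions.

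**What to change.** In SAP 4.2.6.3, 4.2.6.4 and 4.2.6.5, extend the upper limit to include the SFU visit when it is held within its 30 (+7)-day window, that is up to day 37. Keep the existing stop at the start of subsequent or crossover therapy. Align the on-treatment definition in protocol 9.4.2. Because the final analysis has been done, a supplementary summary of these three data types with the 37-day cut, labelled as such in the CSR, would suffice.

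Leave the 30-day treatment-emergent AE definition and protocol Table 13 as they are. Non-serious AEs with onset after day 30 were not systematically collected. A longer AE window would also conflict with protocol 9.5.2 and would be introduced after unblinding.

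The cost is a short wording change and one programming cut-off, since the scheduled SFU measurements are already collected. The downside is that the window for these summaries lengthens by up to 7 days, so a few more off-treatment abnormalities may be counted.
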